**Scientific consultants:**

Ph.D., associate professor, [name]

[contact]

e-mail: [contact].

Doctor of Medical Sciences, [name] [name]

**Foreign consultant:** MD, PhD, professor [name] (Poland)

**Name and address of the organization where the research is being conducted:** Karaganda State Medical University, department of resuscitation, anesthesiology and emergency medicine. Karaganda, [name] and KGP OOD [name].

**Name and address of the laboratory involved:** Research Center Laboratory of the Karaganda State Medical University, Karaganda, [name]

**Brief Summary:** A pressing concern involves the efficient and intensive treatment of complications arising from malignant tumors in the hepatopancreatoduodenal region. This matter is closely tied to rectifying energy deficits, addressing insufficient body weight, and restoring proper metabolic processes. This is particularly crucial post-surgery, as the process is hindered by significant hypercatabolism, heightened nutritional requirements, and the presence of intoxication syndrome.

**Methods.** An investigation was carried out on 91 individuals aged 18 years and older who were afflicted with malignant tumors situated in the hepatopancreatoduodenal area. These patients were categorized into three distinct groups, each receiving a different form of nutritional assistance.

The assessment encompassed various aspects of the patients' nutritional well-being, including outcomes from the screening protocol, body mass index, basal metabolic rate, and critical laboratory measurements such as blood lymphocyte count, total protein level, total bilirubin concentration, as well as ALaT and ASaT levels.

**Keywords:** nutritional status, nutritional deficiency, nutritional support, sips, oncology, nutrition, tumors of the hepatopancreatobiliary zone.

## **I. Purpose of the study and introduction.**

**Purpose of the study.** Comparative analysis of the degree of influence of isolated enteral, isolated parenteral and mixed type of nutritional support on the nutritional status of cancer patients after operations performed in the hepatopancreatoduodenal zone in connection with malignant neoplasms in the early postoperative period.

### **Research objectives:**

1. To conduct a comparative assessment of the dynamics of nutritional deficiency and nutritional status of patients operated on for malignant tumors of the hepatopancreatoduodenal zone in the early postoperative period during isolated enteral, isolated parenteral and mixed types of nutritional support.
2. To analyze the dynamics of the state of protein and carbohydrate metabolism, the consistency of liver function in cancer patients operated on for malignant tumors of the hepatopancreatoduodenal zone, against the background of isolated enteral, isolated parenteral and mixed type of nutritional support in the early postoperative period.
3. To determine the degree of effectiveness of these methods of nutritional support in this category of patients based on the totality of the results of assessing nutritional status and the dynamics of the level of basal metabolism in patients in the early postoperative period.

**Introduction.** Treatment of malignant tumors of the hepatopancreatobiliary zone is one of the most pressing problems in clinical oncology. Among diseases of the liver and extrahepatic biliary tract, the most severe can be considered those that are accompanied by persistent obstruction of the main bile ducts with the subsequent development of obstructive jaundice (MJ), the treatment of which is still controversial.

Despite the increased availability of various highly sensitive non-invasive methods for diagnosing tumors of these organs, the detection of cancer of these organs in the early stages of the disease has practically not increased. In the vast majority of cases, patients continue to be admitted to specialized hospitals only with the development of various complications of cancer of the pancreatoduodenal zone, such as obstructive jaundice, duodenal obstruction, hepatic-renal failure, tumor invasion of hollow organs and bleeding into the lumen of the gastrointestinal tract (Patyutko Yu.I., Kotelnikov A.G., 2007).

43-87% of patients with malignant neoplasms of various localizations have pronounced disturbances in body composition, which correlate with the prevalence of the tumor process and are aggravated during combined treatment. This is based on disturbances in protein, carbohydrate and fat metabolism caused by the systemic effect of the tumor on the body. Violation of nutritional status has a significant impact on the outcome and prognosis of the disease, inevitably increases the duration and cost of treatment, contributes to an increase in mortality and the number of complications, such as infection, slower wound repair, immunosuppression, hemocoagulation disorders, decreased concentrations of blood plasma proteins and a number of enzymes, metabolic disorders medications, decreased tolerance to surgical treatment, radiation and chemotherapy. BUT. Stadley showed that when depleted patients lost 20% of their initial body weight, mortality after surgery reached 33%, and in non-depleted patients -3.5%. According to B.R. Bistrian, G.L. Blakburn, with a 5% decrease in body weight during hospital stay, the length of stay increases by 2 times, and the frequency of complications increases by 3.3 times. J.L. Mullen and G.P. Buzby (1980) showed that impaired nutritional status in surgical patients leads to an increase in postoperative complications by 6 times, and mortality by 11 times, while timely administration of adequate nutritional therapy to such depleted patients reduces the number of postoperative complications by 2-fold. 3 times, and lethality - 7 times.

In this regard, the importance of accurately assessing the nutritional status of patients is obvious, which is the first step in treating and preventing further progression of malnutrition. A variety of methods are used to assess a patient's nutritional status. The use of enteral nutrition in the postoperative period contributes to the rapid elimination of intestinal paresis, early activation of intestinal motility, improved regeneration of the intestinal mucosa and activation of its absorption function.

The possibility of preventing excessive microbial contamination of the gastrointestinal tract, a preventive effect against acute erosive and ulcerative injuries, stopping the catabolic direction of metabolism, normalizing the immune status, reducing the number of infectious complications, reducing the time of stay of patients in the hospital were also noted [Bakhman A L, 2001, Shcherbakova GN, 1996, Kostyuchenko AL, 2001, Grämling L, 2004, Mertes N, 2000, Komplan L, 1999]. There are difficulties in developing protocols and methods for assessing nutritional status and the effectiveness of enteral nutrition in the early postoperative period in patients with hepatopancreaticobiliary diseases.

To solve the problems of perioperative nutritional support during extensive surgical interventions on the abdominal organs, aimed at eliminating metabolic disorders and fully meeting the energy-plastic needs of the body, as well as to eliminate preoperative nutritional deficiency, both parenteral and enteral nutrition are used [Levit D.A., 2008, Davidson, W., 2004, Olofsson B., 2007, Awad S., 2012].

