## **II. Criteria for selecting study participants.**

### **1. Number of participants. (91 patients), will be divided into 3 groups**

1. The first group (n=31) included patients who received enteral nutrition (EN) after surgery.
2. The second group (n=30) included patients receiving parenteral nutrition (PN).
3. The third group (n=30) receiving mixed nutrition (MN), as is commonly considered the method of partial parenteral nutrition, in the early postoperative period.

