## **1. Methods and procedures.**

At the first stage, modern ideas about methods for assessing nutritional status and methods of nutritional support in the early postoperative period of patients operated on for malignant tumors of the hepatopancreatoduodenal zone were studied.

At the second stage, taking into account the need to select the optimal method of nutritional support in the early postoperative period, patients underwent an intragroup and intergroup comparative analysis of the main clinical and laboratory indicators, reflecting the most satisfactory dynamics of plastic processes regarding the type of nutritional support: enteral, parenteral and mixed.

To solve these problems, a prospective, longitudinal, parallel study and retrospective analysis of the results of treatment of 91 patients with malignant tumors of the hepatopancreatoduodenal zone who underwent the following operations were carried out:

- 1) resection of various segments of the liver;
- 2) hemihepatectomy;
- 3) transhepatic drainage of the right and left hepatic duct;
- 4) bypass gastroenteroanastomosis or cholecystoenteroanastomosis with interintestinal enteroenteroanastomosis according to Brown;
- 5) gastro-pancreatoduodenal resection;
- 6) corporecaudal resection of the pancreas with splenectomy.

The study was carried out on the basis of the KGP at the RVC "Multidisciplinary Hospital No. 3 of the city of Karaganda". Venue: intensive care unit.

To identify nutritional deficiencies, there are screening methods recommended by the international clinical nutrition associations ASPEN (American Society for Parenteral and Enteral Nutrition - ASPEN) and ESPEN (European Society for Parenteral and Enteral Nutrition - ESPEN), including questioning patients, using standard anthropometric and laboratory data, which makes it possible to assess nutritional status and the degree of its impairment.

At the first stage, the clinical condition of the patient was assessed using the Nutritional Risk Screening (NRS, 2002), Subjective Global Assessment (SGA) and Nutritional Risk Index (NRI) protocols before surgery and on the 5th, 10th, 15th day after surgery .

A comparative assessment of the clinical effectiveness of the use of types of nutritional nutrition in a complex of therapeutic measures after these operations in the hepatopancreatoduodenal zone was carried out.

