Some nutritional status indicators available for determination at the Oncology Clinic were assessed - body mass index (weight measurements were carried out before surgery, on the 5th, 10th and 15th days), basal metabolic rate (calculated using the Harris-Benedict equation, based on anthropometric data of the patient (gender, age, weight and height).), laboratory parameters: blood hemoglobin, lymphocytes, total protein, serum albumin, serum transferrin, total bilirubin and direct, ALT, AST, which are related to the traditional method for assessing nutritional status.

Additionally, we assessed the duration of postoperative gastostasis, the timing of the onset of intestinal motility, the appearance of stool, the return to a normal diet, the length of patients' stay in the ICU, the readmission of patients to the ICU and the duration of the postoperative bed-day, and the incidence of complications was calculated.

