This fact was obviously associated with the preservation/restoration of parietal digestion in the gastrointestinal tract in the early postoperative period, despite postoperative intestinal paresis of varying degrees, and the involvement of nutrients in anabolic processes with parallel “covering” of the required daily caloric intake by parenteral administration of mixtures.

Evaluation and subsequent analysis of the results of laboratory examination in groups of patients in a comparative aspect showed a relatively slow and gradual decrease in the level of total blood protein by the 5th day of the postoperative period, on average, by  $6.8 \pm 0.95\%$  of the initial values, which,

apparently, was due to increased catabolism and ongoing protein losses (exudation, drainage, etc.) with a fairly significant increase by the end of nutritional support.

Thus, a statistically significant increase in the level of total blood protein was noted in the mixed nutrition group ( $p = 0.004$ ). In the groups with enteral and parenteral nutrition, differences in the dynamics of total protein levels were found at the level of a statistical trend:  $p=0.108$  and  $p=0.129$ , respectively.

When analyzing changes in the number of blood lymphocytes, it should be noted that before the operation the relative value of lymphocytes in the groups was significantly reduced ( $25.9\pm3.7\%$ ), but taking into account the methods and volumes of the operation, the tension of the cellular and humoral parts of the immune system, the dynamics of their level was expressed in the form of a statistically significant increase in the level of lymphocytes in the postoperative period by 10-12 days.

Thus, there was a steady increase in the level of blood lymphocytes by the 10th day of the postoperative period in all groups, on average by 8.95% ( $p = 0.000$ ), by 10.35% ( $p = 0.003$ ), by 10.91% ( $p = 0.000$ ) respectively.

This dynamics reflects the positive effect on the immune status of patients of the combined use of parenteral and enteral types of nutritional support in the postoperative period in this group of patients.

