### **Conclusion:**

1. According to the NRI nutritional status assessment scales, the SGA mixed type of nutritional support at the time of transfer of patients to the specialized department and upon completion of this area of intensive therapy in the specialized department by 12-15 days of the postoperative period showed higher effectiveness in stabilizing the condition and maintaining the patients' caloric intake in a comparative aspect with the group of isolated enteral nutrition and parenteral nutrition.
2. Throughout the entire period of isolated enteral, parenteral and mixed nutritional support, all patients (100%) showed a relatively constant level of total blood protein.
3. In patients of all three groups, throughout the entire period of nutritional support, fluctuations in the level of basal metabolism were observed, which was due to the variability of body mass index and the dynamics of the temperature curve after surgery. In patients in the groups with enteral and parenteral nutrition, by the end of nutritional support (days 15-20), the level of basal metabolism was observed to approach its initial values. With a mixed type of nutrition, a statistically significant decrease in the level of basal metabolic rate was observed, which suggests a more effective coverage of the energy costs of patients with this option of replenishing nutritional ingredients.

**Researcher:** [name], PhD student KSMU

[contact].

e-mail: [contact].

[figure not shown]
Signature  17.03.2020

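### Effectiveness is judged on the whole body of results, with no lead outcome or day and no adjustment across about 150 between-arm tests, so the superiority statements for mixed feeding are exploratory

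*Combined protocol and SAP*

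**What the plan says.** Research objective 3, in the protocol and again in the report, sets the basis for deciding between enteral, parenteral and mixed feeding: "based on the totality of the results of assessing nutritional status and the dynamics of the level of basal metabolism". Neither version names a lead outcome, an analysis day or a way to combine results.

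Methods and procedures lists what is measured:

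- three screening scales (NRS-2002, SGA, NRI), "before surgery and on the 5th, 10th, 15th day after surgery";
- body mass index, where "weight measurements were carried out before surgery, on the 5th, 10th and 15th days";
- the Harris-Benedict estimate of basal metabolic rate, derived from anthropometry;
- "laboratory parameters: blood hemoglobin, lymphocytes, total protein, serum albumin, serum transferrin, total bilirubin and direct, ALT, AST";
- eight recovery outcomes, from gastrostasis to the incidence of complications.

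The protocol's section on data analysis and monitoring names only Student's t-test and Pearson correlation. The report's Methods of statistical data analysis describes a three-group test followed by tests of each of the three pairs of arms. Within arms it describes a test across times followed by tests of each pair of times (baseline, day 5, day 10). Neither section states a significance level or a multiplicity adjustment, and neither says that a non-significant three-group test stops the pairwise tests.

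In the results, "a statistically significant increase in the level of total blood protein was noted in the mixed nutrition group" (p = 0.004), against p = 0.108 with enteral and p = 0.129 with parenteral feeding. Conclusion 1 says that mixed support "showed higher effectiveness in stabilizing the condition and maintaining the patients' caloric intake" compared with the other two routes. Conclusion 3 reads a fall in basal metabolic rate in the mixed arm as better coverage of energy costs.

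**The concern.** When many outcomes are tested on several days and none leads, some differences at p < 0.05 are expected even if the three routes are equivalent. With no combining rule set in advance, the authors can choose, after seeing the data, which results and which days make up the overall judgement.

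The report shows room for such choice. The time point is days 10-12 for the scales, 10-15 for basal metabolism, 12-15 in Conclusion 1 and 15-20 in Conclusion 3. The outcomes also disagree. Bilirubin fell more slowly in the mixed arm by day 5 (20.0%, against 40.09% in the parenteral arm), while total protein is used in favour of mixed feeding. At stake is whether readers take Conclusions 1 and 3 as established superiority or as a pattern picked from many comparisons.

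**Working it through.** The documents state no test count, significance level or power, so there is no plan figure to reproduce. The count below is ours.

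**Inputs from the documents**

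- Repeated outcomes (Methods and procedures): 3 scales + body mass index + basal metabolic rate + 9 laboratory values = 14.
- Recovery outcomes (same section): gastrostasis, motility, stool, normal diet, ICU stay, ICU readmission, postoperative bed-days, complications = 8.
- Pairs of arms (report, statistical methods): 3. Arm sizes: 31, 30 and 30.

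**Assumptions**

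- Postoperative days 5, 10 and 15 for every repeated outcome. The documents give these days for the scales and weight only; the report also cites transaminases on days 2-3, 6-8 and 10-12.
- Two-sided level 0.05.

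**Between-arm count**

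14 × 3 days × 3 pairs = 126, and 8 × 3 pairs = 24. Total: 126 + 24 = 150.

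**Expected false positives if no arm differs**

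The expected number is tests × level, which holds whatever the correlation: 150 × 0.05 = 7.5. A named arm is in 2 of the 3 pairs, and half of the chance differences go its way: 7.5 × 2/3 × 1/2 = 2.5.

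**Narrower readings**

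| Reading | Tests | Expected at 0.05 |
|---|---|---|
| All 14 + 8 outcomes, three days | 150 | 7.5 |
| Without the recovery outcomes | 14 × 3 × 3 = 126 | 6.3 |
| Days 5 and 10 only | 14 × 2 × 3 + 24 = 108 | 5.4 |
| Scales, body mass index and basal metabolism only | 5 × 3 × 3 = 45 | 2.25 |
| Strict, valid three-group gate | 14 × 3 + 8 = 50 outcome-day sets | 2.5 sets |

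At level 0.01 the 150 tests still give 150 × 0.01 = 1.5.

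**Chance of at least one false positive**

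If the tests were independent, 1 − 0.95^150 = 99.95%. They are not: basal metabolic rate and body mass index share weight, and the three pairs share arms. A null simulation (arms of 31, 30 and 30; 50 outcome-day sets; 2000 runs per setting) gave:

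| Correlation between outcome-day sets | At least one of 150 | At least one with a strict gate | At least one favouring the mixed arm (ungated) |
|---|---|---|---|
| 0.3 | 98% | 81% | 64% |
| 0.6 | 81% | 51% | 38% |

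**The total-protein result**

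The values 0.004, 0.108 and 0.129 are one per arm and describe change over time within that arm. No between-arm p-value is printed. A small p-value in one arm and larger ones in two others do not show that the arms differ, and adjusting these p-values would not supply the missing comparison.

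**The case against.** Four points on the other side carry weight.

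1. *The three-group step.* The report's methods put a three-group test before the pairwise tests, and a natural reading is that it screens them. A valid strict gate would halve or nearly halve the problem. In a null simulation of the same design, three or more false positives occurred in 96%, 85% and 58% of runs at correlations 0, 0.3 and 0.6 without a gate, and in 64%, 51% and 31% with one. So a reader who infers that the plan almost always yields several false positives goes too far. But the text does not make the step a condition, a t-test cannot serve as a three-group test, and a gate controls error within one outcome and day, not across them.

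2. *The within-arm tests.* A reader might add 14 × 3 arms × 3 time pairs = 126 within-arm tests and quote 276 × 0.05 = 13.8 false positives. The documents do not support using that figure against an arm comparison: these tests compare no arms, and no change after major surgery is an unlikely null.

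3. *The printed p-values.* It is tempting to say that they fail a Bonferroni limit. The basal-metabolism value (p < 0.03) and the scale value behind Conclusion 1 (p < 0.005) are upper bounds, so they cannot be shown to fail. For p = 0.004, the answer depends on the method. In a family of 14 outcomes × 3 arms = 42 tests on one day, ranked fourth after the three lymphocyte values, it would pass the Benjamini-Hochberg limit (4 × 0.05/42 = 0.0048) but not Bonferroni (0.05/42 = 0.0012) or Holm (0.05/39 = 0.0013). This is why one method must be named.

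4. *A lead outcome chosen now.* The study ended in March 2020 and its results are reported. Choosing a lead outcome, or only the two contrasts involving mixed feeding, would add no error control and would favour the arm already declared better.

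**Conclusion.** The point holds. The plan sets no lead outcome, day, significance level, combining rule or adjustment across outcomes and days, and the report then states superiority. Under equivalence, about 7.5 of about 150 between-arm tests would be significant by chance, about 2.5 of them favouring a given arm. The narrowest readings still leave 2.25 expected tests or 2.5 expected outcome-day sets. These figures rest on our count, on the assumed 0.05, and on days 5, 10 and 15 for all repeated outcomes. The protocol's study plan lists further measures, such as urea, creatinine, glucose and immunology, so the count may be low.

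A reader might go further and infer that the findings for mixed feeding are false. The documents do not show that. They show that Conclusions 1 and 3 cannot be read as confirmatory, and that the total-protein result lacks the comparison it is used to support. The change should be made.

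**What to change.** In the report's Methods of statistical data analysis and the results:

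- Report the between-arm comparison for all three pairs, for each listed outcome and day, with exact p-values. Replace bounds such as p < 0.03 and p < 0.005.
- Name one adjustment, Holm, across the listed outcomes and days, and print adjusted p-values beside the unadjusted ones.
- Treat the within-arm tests as descriptive and do not use them to rank the arms. For total protein, give the between-arm comparison.
- State that no primary outcome was pre-specified and that all comparisons are exploratory.
- Reword Conclusions 1 and 3 accordingly.

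Leave the research objectives as they are, and do not name a lead outcome now that the results are known.

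The cost is reanalysis of data in hand and some rewording. The downside is that fewer results will remain significant: the first Holm step over 150 tests is 0.05/150 = 0.00033.

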### Scientific hypothesis

Complete and comprehensive nutritional support for patients operated on for malignant neoplasms of the hepatopancreatoduodenal zone, in the form of various approaches and methods of delivering nutrients to patients in the early postoperative period, allows to improve the functional activity of the gastrointestinal tract of patients, stabilize the level of carbohydrate, protein, basal metabolism, accelerate transfer to full enteral nutrition and reduce the length of stay in the intensive care unit and, ultimately, in the hospital.

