### Research objectives:

1. To conduct a comparative assessment of the dynamics of nutritional deficiency and nutritional status of patients operated on for malignant tumors of the hepatopancreatoduodenal zone in the early postoperative period during isolated enteral, isolated parenteral and mixed types of nutritional support.
2. To analyze the dynamics of the state of protein and carbohydrate metabolism, the consistency of liver function in cancer patients operated on for malignant tumors of the hepatopancreatoduodenal zone, against the background of isolated enteral, isolated parenteral and mixed type of nutritional support in the early postoperative period.
3. To determine the degree of effectiveness of these methods of nutritional support in this category of patients based on the totality of the results of assessing nutritional status and the dynamics of the level of basal metabolism in these patients in the early postoperative period.

Researched 91 patients, will be divided into 3 groups:

1. The first group (n=31) included patients who received enteral nutrition (EN) after surgery.
2. The second group (n=30) included patients receiving parenteral nutrition (PN).
3. The third group (n=30) receiving mixed nutrition (MN), as is commonly considered the method of partial parenteral nutrition, in the early postoperative period.

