As can be seen from the presented data, in the preoperative period, according to the SGA assessment, 24 patients in the enteral group, 19 patients in the parenteral group, and 17 patients in the mixed group had normal nutritional status before surgery, with variations relative to patients with moderate to severe malnutrition. Assessment of nutritional status before surgery using the NRI scale allowed us to confirm the nutritional status of the vast majority of patients in all groups as relatively normal

Thus, in 62 of the 91 patients examined, the NRI was assessed as true negative (normal nutritional status), in 26 as true positive (moderate malnutrition), and in 3 as severe malnutrition. Data from the NRI method during this time period had a strong correlation with the results of the SGA scale ( $p < 0.005$ ).

On the 10-12th day of the postoperative period in patients of the “enteral” group, the results of the assessment on the SGA scale remained unchanged; according to the NRI rating scale, there was an increase in “moderate malnutrition” per patient (25%).

With parenteral nutritional support, 17 patients had “normal nutrition”, 14 patients had moderate malnutrition, with regression of “severe malnutrition” in 1 patient. In the mixed nutrition group, there was a complete elimination of signs of “severe malnutrition” by 100% according to the given scales ( $p < 0.005$ ).

In patients of all study groups, throughout the entire period of nutritional support, fluctuations in the level of basal metabolism were observed in average values of  $335.89 \pm 53.6$  kcal/day (13.44%) from the initial value - 1-2 days of the postoperative period and were due to variability body mass index and the dynamics of the temperature curve after surgery.

In patients in the groups with enteral and parenteral nutrition, by the end of these types of energy subsidies (days 10-15), the level of basal metabolism was observed to approach its initial values -  $2500.1 \pm 353.4$  kcal/day and  $2350.0 \pm 330.5$  kcal/day days accordingly. With a mixed type of nutrition, there was a statistically significant decrease in the level of basal metabolism by 6.78% ( $2250.0 \pm 105.2$  kcal/s), which allows us to conclude that patients' energy costs are more effectively covered with this option of nutritional support in a comparative aspect with isolated types nutrition ( $p < 0.03$ ).

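### Basal metabolism is used to judge feeding with no stated direction of benefit, so the claim that mixed feeding covers energy costs more effectively is not supported

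*Combined protocol and SAP*

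**What the plan says.** Research objectives, item 3, in section I of the protocol names two grounds for judging the feeding methods: the nutritional-status assessments, and "the dynamics of the level of basal metabolism in patients in the early postoperative period". The report repeats the objective almost word for word ("the dynamics of the level of basal metabolism in these patients in the early postoperative period"). Neither version gives a favourable direction, a target or a threshold, and neither statistics section supplies one.

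The Scientific hypothesis, which appears only in the report, does imply a direction: nutritional support should "stabilize the level of carbohydrate, protein, basal metabolism".

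The results, printed under Methods of statistical data analysis, say of enteral and parenteral feeding that "the level of basal metabolism was observed to approach its initial values". For mixed feeding they say that "there was a statistically significant decrease in the level of basal metabolism by 6.78" per cent, "which allows us to conclude that patients' energy costs are more effectively covered with this option of nutritional support". Conclusion, item 3, repeats the claim: "a statistically significant decrease in the level of basal metabolic rate was observed, which suggests a more effective coverage of the energy costs".

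Protocol section III (Methods and procedures) and the report's Clinical research program both state that basal metabolic rate was calculated with the Harris-Benedict equation from sex, age, weight and height. It was not measured.

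**The concern.** An outcome without a stated direction cannot rank treatments, because any arm that differs can afterwards be called the better one. Here the report contains two directions. The hypothesis treats a stable value as the aim. The results and Conclusion 3 treat a fall as the better outcome and place the arm that fell above the two that moved back towards their starting level. Nothing connects the two criteria.

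Objective 3 is the study's effectiveness objective. Of the three conclusions, only items 1 and 3 favour mixed feeding, so one of the two supports for the study's main message rests on this reading.

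**Working it through.** **Inputs.** From the report's results: end values of 2500.1 ± 353.4 kcal/day (enteral), 2350.0 ± 330.5 (parenteral) and 2250.0 ± 105.2 (mixed; the unit is printed as kcal/s and is read here as kcal/day); a mixed-arm fall of 6.78%; and an average fluctuation over all groups of 335.89 kcal/day, given as 13.44% of the initial value. From protocol section II: 31, 30 and 30 patients.

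**1. The 6.78%.** It cannot be reproduced, because no arm's initial value is printed. Assuming that it is measured against the mixed arm's own initial value:

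- initial = end / (1 − fall) = 2250.0 / (1 − 0.0678) = 2413.6 kcal/day
- fall = 2413.6 − 2250.0 = 163.6 kcal/day

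Rounding of the percentage (6.775 to 6.785) moves the initial value only between 2413.5 and 2413.8.

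**2. A second implied baseline.** The all-group figure gives 335.89 / 0.1344 = 2499.2 kcal/day. Against that, the mixed arm's change would be (2250.0 − 2499.2) / 2499.2 = −9.97%, not −6.78%. The two figures agree only if the arms started at different levels or the 6.78% has some other reference.

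**3. Illustration with a common baseline.** Change = (end − initial) / initial:

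| Assumed initial, all arms | Enteral | Parenteral | Mixed |
|---|---|---|---|
| 2499.2 | +0.04% | −5.97% | −9.97% |
| 2413.6 | +3.58% | −2.64% | −6.78% |

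In both rows mixed feeding comes first if a fall is good and last if stability is good. The order of enteral and parenteral feeding on stability changes between the rows.

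**4. Why this is only an illustration.** A common starting level is not documented. The parenteral arm would have moved by more than 6.78% if it started above 2350.0 / 0.9322 = 2520.9 or below 2350.0 / 1.0678 = 2200.8 kcal/day. For the enteral arm the limits are 2500.1 / 0.9322 = 2681.9 and 2500.1 / 1.0678 = 2341.4. The first of these limits is only 2520.9 − 2499.2 = 21.7 kcal/day above the all-group figure. Saying that values approached the initial level does not exclude such starting points.

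**5. What can move the calculated value.** Of the four inputs, sex and height are fixed and age hardly changes in 10 to 15 days. Within a patient, a fall can therefore arise essentially only from a lower weight. The introduction cites a 5% loss of weight in hospital as going with twice the length of stay and 3.3 times the complications. The results also attribute the fluctuations to the temperature curve, which is not a listed input.

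**6. The printed p < 0.03.** The comparison tested is not stated. Two-sample t tests on the printed end values, mixed against parenteral, give p = 0.12 if ± is a standard deviation and 0.77 if it is a standard error. Mixed against enteral gives about 0.0005 and 0.50. End values alone therefore do not support p < 0.03 against both isolated methods. The printed value may come from a within-group test, which would not compare arms.

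**The case against.** The best defence concerns the starting point. The results mention postoperative days 1 and 2 beside the initial value, and the brief summary describes marked hypercatabolism after surgery. If the initial value is an early, raised one, a fall could be recovery, and so a form of stabilisation. This softens the conflict and cannot be excluded. The documents lean the other way: weight was scheduled before surgery and on days 5, 10 and 15, not on days 1 or 2, and the bilirubin paragraph explains initial values as preoperative. Even if the defence is right, nothing states that criterion in advance.

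The report also offers a reason for crediting the fall: preserved digestion in the gut while parenteral mixtures supply the remaining calories. That is a mechanism offered after the result. It does not explain how a fall meets an aim of stability.

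A reader might go further and infer that, on the study's own hypothesis, enteral and parenteral feeding succeeded, mixed feeding failed and the ranking reverses completely. The documents do not support that. They print no arm's initial value and no threshold for stability, and the 13.44% average fluctuation over all groups is about twice the mixed arm's 6.78%. The hypothesis ranks no arm. A reader might also infer that a prespecified criterion was swapped once the results were known. The hypothesis appears only in the report of March 2020, beside the results, so stability cannot be shown to have been prespecified any more than a fall.

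**Conclusion.** The concern holds in a limited form. Objective 3 sets no direction of benefit, the hypothesis and the conclusion use different ones, and the report does not reconcile them. The claim in the results and Conclusion 3 that mixed feeding covers energy costs more effectively is therefore unsupported. It is weakened further because the calculated value can fall within a patient essentially only through weight loss.

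The fall is about 163.6 kcal/day from about 2413.6 kcal/day, assuming that the 6.78% refers to the mixed arm's own initial value. The opposite claim, that the result counts against mixed feeding, is not established either: the ranking on stability depends on initial values that are not printed. The direction, the reference time and the initial values all remain open.

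**What to change.** - In the results and Conclusion 3, withdraw the inference that the fall shows more effective coverage of energy costs. Report the changes in basal metabolism descriptively, without ranking the arms.
- State which time point the initial value refers to, and print each arm's initial and end values. The end of support also needs one definition: the results give days 10 to 15 and Conclusion 3 gives days 15 to 20.
- Tabulate change by arm. If stability is the criterion, use absolute percentage deviation from the initial value and show signed change alongside. A mean signed deviation alone will not do, because +10% and −10% average to zero and an unstable arm would look stable.
- Reconcile the hypothesis, the results and Conclusion 3. The study ended in March 2020, so any direction of benefit adopted now must be labelled post hoc.

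The cost is the loss of one claim in favour of mixed feeding, some rewording and one re-tabulation of existing data.
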